6. CLINICAL SITES

This study will be conducted at multiple centers by experienced, high-volume surgeons in the United States

7. PATIENT SELECTION

Enrollment: Approximately 500 patients will be enrolled and followed for a period of 24 months in order to assess patient outcomes. Each center is expected to enroll approximately 100 patients (50 in each group). The investigator is responsible for evaluating each patient against the following criteria and assuring that the patient meets the following requirements in order to be enrolled in the study. Each patient must meet all the inclusion criteria and none of the exclusion criteria to be considered for enrollment.

7.1 Patient Eligibility

a. Inclusion Criteria

- Patients who meet the indications for use for primary PCL-retaining TKA using the Triathlon® Total Knee System using VERASENSE™
- Subject must be diagnosed with one or more of the following conditions
 - osteoarthritis
 - rheumatoid or other inflammatory arthritis
 - post-traumatic arthritis
- Subject is likely to be available for all study visits
- Subject is able and willing to sign the informed consent and follow study procedures

b. Exclusion Criteria

- Prior Total Knee Arthroplasty
- Avascular Necrosis
- Any knee surgery other than meniscectomy (can be arthroscopic or open)
- Ligament insufficiencies, prior surgeries such as ACL or PCL reconstructions, posterolateral reconstructions, osteotomies, tibia plateau fractures
- Ipsilateral foot/ankle and hip arthritis

- Range of motion less than 90°, flexion contracture greater than 20°
- Subject has a mental condition that may interfere with the subject's ability to give an informed consent or willingness to fulfill the study requirements (i.e., severe mental retardation such that the Subject cannot understand the informed consent process, global dementia, prior strokes that interfere with the Subject's cognitive abilities, senile dementia, and Alzheimer's Disease)
- Any subjects meeting any contraindication criteria as identified in the locally approved labeling for the device should be excluded from this study.

7.2 Contraindications for the Triathlon™ Knee are:

1. Any active infection or suspected latent infection in or about the knee joint
2. Distant foci of infection which may cause hematogenous spread to the implant site
3. Any mental or neuromuscular disorder which would create an unacceptable risk of prosthesis instability, prosthesis fixation failure, or complications in post-operative care
4. Bone stock compromised by disease, infection or prior implantation that cannot provide adequate support and/or fixation to the prosthesis
5. Skeletal immaturity
6. Severe instability of the knee joint secondary to the absence of collateral ligament integrity and function
7. Obesity. An overweight or obese patient can produce loads on the prosthesis that can lead to failure of fixation of the device or to failure of the device itself

7.3 Patient Failure / Withdrawals

Removal or revision of any implant or malfunction of VERASENSE™ intra-operatively will be considered endpoints, with the patient being withdrawn from continued follow-up in the study. Every attempt must be made to ensure that all patients return for all of the post-operative assessments. However, patients are free to withdraw from the trial at any time and are under no obligation to provide a reason for doing so. All attempts should be made to ascertain whether a patient is lost to follow up, chosen not to return for follow-up or is deceased.

8. Medical Device Adverse Clinical Event Reporting

This study is not intended to prospectively assess the absolute product safety; however any device or procedure related safety issues will be documented as follows. The site will be required to transcribe onto the Safety Data CRF only those adverse clinical events that have been determined by the physician investigator to be attributable (even remotely) to 1) the knee arthroplasty procedure and/or 2) the use of the VERASENSE™ device.

The information to be captured on the CRF include the severity, relationship to knee arthroplasty procedure and the VERASENSE™ Device, outcome and treatment (when applicable).

a.

Expedited Reporting - Medical Device Reportable Events (21 CFR §803.3)

Expedited reporting to OrthoSensor is required for any fatal or serious injury (as defined below) that in the judgment of the physician investigator may have been attributed to the use of the VERASENSE™ device (only), or that the device was or may have been a factor in a death or serious injury, including events occurring as a result of: (1) failure; (2) malfunction; (3) improper or inadequate design; (4) manufacture; (5) labeling; or (6) user error.

The term “Serious injury” is defined per 21 CFR 803 as an injury or illness that:

1. Is life-threatening
2. Results in permanent impairment of a body function or permanent damage to a body structure;
3. Necessitates medical or surgical intervention to preclude permanent impairment of a body function or permanent damage to a body structure

The clinical site must notify the OrthoSensor by email or telephone immediately but no later than 2 business days of any fatal or serious injury directly attributed to the use of the VERASENSE™ device. Notification to the IRB of record will be done according to the IRB’s specific procedures. OrthoSensor will be responsible for reporting the event to the FDA according to the timelines put forth in 21 CFR 803.

8.1 Risk Benefit Analysis:

As in any surgical procedure, certain risks are associated with total joint arthroplasty. These risks include but are not limited to: anaesthetic and post-anaesthetic reactions (such as hyperaemia), allergic reactions to prophylactic antibiotics or blood transfusions, damage to blood vessels or nerves or death. Post-operatively, a patient may experience thrombophlebitis, pulmonary embolus, dislocation, pain, limp, component loosening, osteolysis due to wear debris or the need for additional surgery. Fracture of the prosthesis is a potential complication.

As all patients recruited for this study are indicated for primary total knee arthroplasty with the device described in the protocol anyway, there is no known risk associated with participating in this study.

8.2 Protocol Departures:

Any departure from the current, approved protocol is considered to be a deviation or violation. Depending on severity of the departure, the reporting timeframe for the deviation/violation will change.

The following definitions apply:

- **Violation:** protocol deviation that is IRB/FDA reportable. For example, but not limited to, Informed Consent Documents not signed before surgery, a missing or lapsed IRB approval or an ineligible subject enrolled
- **Deviation:** protocol is not being followed exactly. For example, but not limited to, visits out of window, some data not collected for that visit or source documentation not available for a visit (CRFs used as source document).

8.3 Informed consent violation:

No patient will be enrolled in the study and have any study-related procedures performed, including completing subject clinical assessments, before an approved Informed Consent Document is signed. If this occurs, this is a VIOLATION and must be reported to OrthoSensor.

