The latest version of the KSS was developed in 2011 and introduced by the Knee Society. The latest version of the KSS originates from the popular KSS (from 1989); both physician and patient derived. It includes versions administered preoperatively and postoperatively. It has an initial assessment of demographic details, including an expanded Charnley functional classification. The objective knee score, completed by the surgeon, includes a VAS score of pain, walking on level ground and on stairs or inclines, as well as an assessment of alignment, ligament stability and ROM, along with deductions for flexion contracture or extension lag. Patients then record their satisfaction, functional activities, and expectations. Given the diverse activity profiles of many contemporary patients, the functional component of the score was improved to include a patient-specific survey, which evaluates features such as standard activities of daily living, patient-specific sports and recreational activities, patient satisfaction, and patient expectations. The new Knee Society Knee Scoring System has been developed and validated, in part, to better characterize the expectations, satisfaction, and physical activities of the younger and more diverse population of current patients undergoing TKA. The score was validated in a thoughtful and methodical fashion confirming internal reliability and analyzed for differential item functioning. The new Knee Society Scoring System is broadly applicable across sex, age, activity level, and implant type. Completing the questionnaire takes 10 to 30 minutes.
- **Forgotten Joint Score (FJS)**
The FJS is a patient reported outcome measure, consisting of 12 questions (e.g. awareness traveling in a car or climbing stairs?). It uses a 5-point Likert response format and the raw score is transformed to range from 0-100 points. High score indicates good outcome, e.g. a high degree of forgetting the joint in everyday life (forgotten joint phenomenon). The FJS has a low ceiling effect and was designed to discriminate between good, very good and excellent outcomes after TKA.
- **Knee Pain Evaluation Form**
The knee pain evaluation will be used to assess the prevalence and location site of knee pain when applicable. This evaluation will be completed by the investigator post total knee surgery during the intervals defined in Table 1 “Schedule of study assessments”.

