- Radiographic evaluation via Mediolateral and anteroposterior x-rays as is standard of care. The prevalence and location of radiolucency and/or osteolysis is evaluated on both AP and lateral views at each patient’s routine postoperative

follow-up visits. These evaluations are performed by each patient's operating surgeon.

- Complications, adverse events, and survivorship data will be collected and reported. This information will be gathered at each of the study follow-up visits.

c. Data Collection Periods:

Data will be collected pre-operatively, intra-operatively, and post-operatively at 6 weeks, 6 months, and 1 year. All time point windows are determined using the date of surgery (DOS) as day 0, including all annual visits. The visit windows are as follows:

Pre-operative: within 3 months prior to the date of the surgery excluding

*Pre-operative radiographs. Pre-operative radiographs taken within 12 months of scheduled knee replacement surgery are sufficient.

Intra-operative: within 2 weeks after the date of surgery

6 weeks: DOS + 6 weeks ± 4 weeks

6 months: DOS + 6 months ± 45 days

1 year: DOS + 1 year ± 90 days

2 year: DOS + 2 year ± 90 days

Table 1. Schedule of study assessments

Data Collected	Pre-op Baseline	Operative Discharge	6 Weeks	6 Months	1 Year	2 Years
Obtain Written Informed Consent	X					
Demographics	X					
Intra Operative		X				
EQ-5D	X		X	X	X	X
New-KSS	X		X	X	X	X
FJS			X	X	X	X
Knee Pain Evaluation Form				X	X	X
Radiographic Alignment	X		X	X	X	X
Adverse Event Reporting (When Present)		(X)	(X)	(X)	(X)	(X)

10. Analysis to be Performed on Data (e.g. Statistical Analysis)

Analysis of the data will be performed using SPSS version 21. Comparative Statistics will be run between outcomes data stratified by both groups: Analysis of variance (AVOVA) will be used to assess the difference between each group, with post-hoc t-tests to demonstrate significance. Separate analyses will be performed to evaluate power of sample sizes and any correlative affect that demographic/clinical variables may have on patient outcomes.

11. Monitoring of data collection

The Sponsor will monitor all data collected for accuracy and completion. The site will be monitored at least once per calendar year following the initial/first-monitoring visit.

12. Patient Identification

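### Patients are withdrawn from follow-up after implant revision or sensor malfunction, so their later pain and function scores are never collected and no planned analysis addresses the loss

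*Combined protocol and SAP*

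**What the plan says.** Section 7.3 sets the rule: "Removal or revision of any implant or malfunction of VERASENSE™ intra-operatively will be considered endpoints, with the patient being withdrawn from continued follow-up". The next sentence pulls the other way, since "Every attempt must be made to ensure that all patients return for all of the post-operative assessments", but it makes no exception for patients the rule has withdrawn. The section treats voluntary withdrawal separately ("patients are free to withdraw from the trial at any time"), so the first rule is imposed by the protocol and is not a patient's choice.

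Section 9 adds that "Complications, adverse events, and survivorship data will be collected and reported", and says this information is gathered at the follow-up visits. Table 1 schedules EQ-5D, KSS and FJS at 6 weeks, 6 months, 1 year and 2 years, and the Knee Pain Evaluation Form from 6 months. Pain is captured twice: "The objective knee score, completed by the surgeon, includes a VAS score of pain", and "The knee pain evaluation will be used to assess the prevalence and location site of knee pain when applicable".

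Section 10 plans an analysis of variance that "will be used to assess the difference between each group, with post-hoc t-tests to demonstrate significance", plus evaluations of power and of correlations with patient variables. It names no analysis population, no missing-data method and no sensitivity analysis.

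**The concern.** Removing patients from later assessment because of something that happened after allocation means the later groups are no longer those formed by randomization. The two events differ in importance.

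- **Revision or removal** is the main issue. The Introduction says that poor rotational positioning causes early complications that can end in revision. On the protocol's own reasoning, revision lies on the pathway that sensor guidance is meant to change, so the loss may be related both to group and to outcome.
- **Sensor malfunction** is a smaller issue. The patient leaves on the day of surgery and contributes no post-operative score. Malfunction interrupts guidance in Group B but only a surgeon-blinded recording in Group A (section 5), so it need not be balanced or have the same meaning in the two arms. Because complications and survivorship are gathered at follow-up visits, a later revision in such a patient also has no planned route into the data.

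What is at stake is the part of the section 3 hypothesis on pain, return to activities and satisfaction. The alignment and balance readings from the index operation are not affected by a later revision.

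**Working it through.** **What is kept and what is lost.** After a revision, the study keeps the event, the scores before it (including KSS pain at 6 weeks if the revision came later) and the index-surgery readings. It loses every KSS, FJS, EQ-5D and knee-pain form due afterwards. After a malfunction it loses all post-operative scores.

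**Plan figure.** The sample size of about 500 comes with no alpha, power, effect size or SD, so it cannot be reproduced. The calculations below show scale only.

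**Inputs.** From the documents: 250 per group (section 5), and 20% as the upper figure for anterior knee pain after TKA (Introduction), used here as control-arm pain prevalence. Assumed: 12% pain in the sensor arm; two-sided alpha 0.05; revision rate *r* of 1% to 4%; and *f*, the share of revised patients who would be painful at the later visit, of 100%, 50% or 20%.

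**Pain prevalence.** With *p* the prevalence among all allocated patients, withdrawing the revised leaves

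observed prevalence = (*p* − *f r*) / (1 − *r*), with *n* = 250(1 − *r*) per arm.

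Power is for an unpooled two-sided z-test. With no withdrawal, SE = √[(0.20×0.80 + 0.12×0.88)/250] = 0.0326, and 0.080/0.0326 = 2.45, giving power of 69%.

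Example, revisions 4% in A and 1% in B, *f* = 1: A = (0.20 − 0.04)/0.96 = 0.1667; B = (0.12 − 0.01)/0.99 = 0.1111; difference 0.0556; power 43%.

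| Revisions A vs B | All painful | Half painful | One in five painful |
|---|---|---|---|
| 4% vs 1% | 5.6 points (43%) | 7.1 (60%) | 8.1 (69%) |
| 2% vs 1% | 7.3 (63%) | 7.8 (67%) | 8.1 (69%) |
| 2% vs 2% | 8.2 (74%) | 8.2 (71%) | 8.2 (70%) |
| 1% vs 4% | 10.9 (94%) | 9.3 (83%) | 8.3 (72%) |

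The true difference is 8.0 points throughout; power is in parentheses.

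**No true difference (20% in both arms).** With revisions 1% vs 4% and all revised patients painful: 0.1919 − 0.1667 = 2.5 spurious points in favor of the sensor, and 11% rejection. With half painful: 0.1970 − 0.1875 = 0.9 points and 5.8%. With revisions 1% vs 2%: 5.6% and 5.1% rejection respectively. Equal rates give no bias.

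**Mean scores.** If revised patients would score *k* SD worse, the bias in the group difference is *k* × (difference in revision rates). For *k* = 1 to 2 and differences of 1 to 3 percentage points, this is 0.01 to 0.06 SD. The difference detectable with 80% power is (1.960 + 0.842) × √(2/250) = 0.251 SD.

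**Malfunction.** If it is unrelated to outcome there is no bias. Losing 2% per arm (245 left) or 5% (237.5 left) takes power from 69% to 68% or 67%. If Group B malfunction patients instead carry the control risk of 20%, the as-allocated B prevalence is 0.12(1 − *m*) + 0.20*m* = 12.16% at *m* = 2% or 12.40% at *m* = 5%. The observed figure is 12%, so benefit is overstated by 0.2 or 0.4 points.

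**The case against.** The strongest counter-argument concerns size. The fall to 5.6 points needs a fourfold imbalance in revisions and every revised patient still in pain, and the documents support neither assumption. The 11% false-positive rate likewise needs both extremes together. Elsewhere in the grid the effect is modest or absent. Section 10 also names ANOVA and t-tests, which compare means, and there the bias is at most 0.06 SD in the assumed range. All of this stands, and it keeps the point from being critical. The prevalence calculation is still relevant, because the Knee Pain Evaluation Form is intended to measure prevalence.

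A second argument is that stopping at revision is a legitimate choice of estimand: a later score partly reflects a second operation. The visit timing adds force, because "All time point windows are determined using the date of surgery (DOS) as day 0, including all annual visits", so a score may fall shortly after the revision. This is fair, but the plan states no such estimand. Continued collection also still allows an analysis that censors at revision, whereas stopping collection rules out the alternative.

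Third, failures are counted through the endpoint label and survivorship reporting. That is true, but no rule says how the event enters the comparison of pain or function.

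Fourth, the request that all patients return can be read as covering only those still in follow-up. On that reading it does not contradict the withdrawal rule, but it does not bring withdrawn patients back either. A malfunctioning sensor may also fail to give a usable intra-operative reading. That loss comes from the malfunction itself, and the withdrawal rule neither causes nor repairs it.

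**Conclusion.** The concern holds. As written, section 7.3 makes the later pain and function comparison conditional on post-allocation events, and nothing in section 10 restores the affected patients. The structural point needs no assumed figure. Its size does: with revision rates of 1% to 4%, the observed pain difference ranges from 5.6 to 10.9 points against a true 8.0. It is close to 8.0 when rates are equal or when revised patients are no more painful than others. The direction depends on which arm has more revisions: more in the control arm hides benefit, and more in the sensor arm exaggerates it. Malfunction is a minor part of the point. Confidence is medium because the documents give no revision or malfunction rates. The amendment should be made because the fix is cheap and the loss is irreversible.

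**What to change.** Replace the first sentence of section 7.3 with:

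> Removal or revision of an implant, and intra-operative sensor malfunction, are recorded as events and reported by group. Unless consent is withdrawn, the patient remains in the study and completes all scheduled patient-reported, KSS and knee-pain assessments and adverse-event reporting. The date of any revision is recorded so that the time from revision to each later score is known. All patients are analysed in the group to which they were allocated. Radiographic alignment after a revision is excluded from the alignment comparison. A patient with sensor malfunction only keeps the scheduled radiographs.

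Add two sensitivity analyses to section 10: one that censors scores at revision, and one that counts a revised knee as painful when knee-pain prevalence is compared from the Knee Pain Evaluation Form. The two address opposite assumptions about revised patients and should be read together.

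**Cost.** A short amendment to sections 7.3 and 10, with sponsor, investigator and IRB approval under section 16. The visits are already in Table 1. At the assumed rates the change retains about 3 to 10 revised patients per arm (250 × 0.01 = 2.5; 250 × 0.04 = 10) and about 5 to 13 malfunction patients per arm (250 × 0.02 = 5; 250 × 0.05 = 12.5). Only data collection and analysis change. Post-revision scores will partly reflect the revision; the recorded date and the censoring analysis deal with that.

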4. TREATMENT AND DEVICE

The intervention involves the use of VERASENSE by the surgeon during Total Knee Replacement Surgery. VERASENSE is available for use with the Stryker Triathlon Total Knee System. VERASENSE replaces the standard tibial trial inserts and is embedded with microelectronics and sensors to provide surgeons with real-time knee kinetic data. The data is wirelessly transmitted to a graphic display (VERASENSE Knee Application), allowing surgeons to quantify and assess soft tissue intercompartmental loads throughout the range of motion. The VERASENSE sensor is not an investigational device. OrthoSensor, Inc., received FDA 510K clearance in 2009. The indication for use is a tool for adjustment of the femoral knee

implant to reduce instability from flexion gap asymmetry. The VERASENSE sensor is sterile and single patient use.

4.1 – Description of VERASENSE

- One articulation (Figure 1): Cruciate Retaining (CR); However can be utilized with Posterior stabilizing implant designs
- Six Sizes: 2, 3, 4, 5, 6, 7
- Four attachable shim thicknesses: 9, 11, 13, and 16mm

[figure not shown]
Figure 1 – CR VERASENSE Inserts

4.2 – VERASENSE Knee Application (Figure 2)

- Graphic display is a 27" iMac with keyboard, mouse, bar-code reader, activation magnet, receiver (Antenna)
- Software application provides femoral contact point location and load values for medial and lateral condyles; kinematic tracking; tray rotation, tibia varus/valgus axis; mechanical axis

Figure 2 – Graphic Display

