5. METHODS / PROCEDURES

Patients indicated for TKA and who meet all study eligibility criteria will be asked to participate in the study. Eligible patients will receive a primary unilateral PCL-retaining or – sacrificing TKA using the Stryker Triathlon Total Knee System *with* or *without* the use of the VERASENSE™ Knee System. Patients will be enrolled in a consecutive series consisting of two cohorts (Groups A and B). Both groups are described below:

Group A – Control (Surgeon-Guided) will consist of **250** consecutive patients who will undergo primary unilateral PCL-retaining or – sacrificing TKA using the Stryker Triathlon Total Knee System *without* the use of VERASENSE to guide rotational alignment and balance. **Prior to closing the arthrotomy, VERASENSE will be utilized in a surgeon-blinded fashion to record rotational alignment and intercompartmental pressures through a range of motion.**

Group B (Sensor-Guided) will consist of **250** consecutive patients who will undergo primary unilateral PCL-retaining or – sacrificing TKA using the Stryker Triathlon Total Knee System *with* the use of VERASENSE to guide rotational alignment and balance. The sensor data will be used for balancing per the VERASENSE protocol below.

Each patient will be given a unique study number once informed consent has been obtained. The investigator will be blinded to the patient study number and the patient will be blinded to his/her assigned group. It will be important that all patients remain blinded to their assigned group. The patient will be informed during the consent process that they may or may not receive their knee replacement procedure using the VERASENSE Knee System.

Radiographic outcomes will be assessed on all patients within the first 12 weeks and at the annual visits. Any postop complications will also be monitored.

Surgical Protocol – Using VERASENSE

All knees will be prepared using standard instrumentation and a measured resection or gap balancing technique. The following steps will be performed when using VERASENSE:

Step 1: Establish Tibial Tray Rotation:

Select and position appropriate sized trial tibial tray. Align the tray to the anatomy (mid-medial third of the tubercle) as recommended by the manufacturer's surgical technique. Insert a single anterior or posterior pin (medially or laterally) into the trial tray to allow for internal / external rotational adjustment while maintaining optimal medial / lateral coverage.

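### Section 7.3 gives an intra-operative fault of the trial sensor the same status as removal or revision of an implant, and on neither reading of the rule does the trial obtain implant survival in all operated knees

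*Combined protocol and SAP*

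**What the plan says.** Section 7.3 (Patient Failure / Withdrawals) sets one rule for two events: "Removal or revision of any implant or malfunction of VERASENSE™ intra-operatively will be considered endpoints". The sentence goes on to give the consequence for both: "with the patient being withdrawn from continued follow-up in the study". The rest of the section deals with retention, voluntary withdrawal, loss to follow-up and death.

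Section 9b makes a separate commitment: "Complications, adverse events, and survivorship data will be collected and reported". It gives no event definition, time origin or censoring rule and does not refer to Section 7.3. Section 10 names analysis of variance and t-tests, and no survival method.

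Section 4 describes the device: "VERASENSE replaces the standard tibial trial inserts", and "The VERASENSE sensor is sterile and single patient use". It is used at trialling and is not part of the implanted prosthesis.

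Section 5 uses the sensor in both arms. For Group A, "VERASENSE will be utilized in a surgeon-blinded fashion to record rotational alignment and intercompartmental pressures" before closure. For Group B, "The sensor data will be used for balancing per the VERASENSE protocol below".

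**The concern.** The two events differ in kind. Removal or revision is evidence about the implant. A sensor that fails during trialling is evidence about an instrument that leaves the operating room with the packaging. Section 7.3 treats them alike, and it is the only place in the text available to me that looks like a failure definition. An analyst asked for survivorship could therefore use it, or could use something else, and two analysts could report different figures from the same data.

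What is at stake is which knees enter the survivorship figure and how they are counted. Revisions after primary knee replacement may well be few in a 2-year trial of 500 patients. If so, even a handful of sensor faults could be a large share of the events.

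**Working it through.** The plan gives no revision rate, malfunction rate or survivorship figure, so there is nothing of its own to reproduce. The only input from the documents is 250 patients per arm, 500 in all (Section 5). Everything else is assumed: 2-year revision risk r = 2% in both arms (also 1% and 3%), and intra-operative malfunction risk m = 0.5% to 2%.

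**Step 1: apply the rule to three patients.**
- Revised at month 14: an endpoint at month 14, on any reading.
- Sensor loses signal at trialling, implant sound: either a failure on day 0, or out of the study on day 0.
- Neither event: followed to 2 years.

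Only the second patient's status depends on the reading. On neither reading is that patient's implant status at 2 years observed.

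**Step 2: 'endpoints' means failure.** Apparent failure = m + (1 − m)r. The share due to the sensor = m / [m + (1 − m)r]. With r = 2%, true implant survival is 98.0%.

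| m | Apparent failure | Apparent survivorship | Sensor faults among 500 | Share of counted failures |
|---|---|---|---|---|
| 0.5% | 0.005 + 0.995 × 0.02 = 0.0249 | 97.5% | 2.5 | 20% |
| 1% | 0.01 + 0.99 × 0.02 = 0.0298 | 97.0% | 5 | 34% |
| 2% | 0.02 + 0.98 × 0.02 = 0.0396 | 96.0% | 10 | 51% |

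At m = 1%, changing r to 1% gives 98.0% against a true 99.0% (sensor share 50%). Changing r to 3% gives 96.0% against a true 97.0% (share 25%).

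**Step 3: 'endpoints' means end of participation.** Knees lost on day 0 = 500m = 2.5 to 10. If their revision risk equals that of the others, survivorship among the remaining knees is still 1 − r = 98.0%, and the expected number of unseen revisions is 500 × m × r = 0.05 to 0.2. The bias is then negligible, but the trial cannot check that condition. Without it, survival in all operated knees is known only to lie between (1 − m)(1 − r) and (1 − m)(1 − r) + m. At m = 2% that is 0.98 × 0.98 = 96.0% to 0.9604 + 0.02 = 98.0%. The lower limit equals the Step 2 figure: the failure reading amounts to assuming that every knee with a sensor fault had a failed implant.

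**Step 4: by arm, on the failure reading with r = 2%.**
- m = 1% in both arms: 97.0% and 97.0%, difference zero.
- m = 1% in Group A and 2% in Group B: 97.0% and 96.0%. A nominal two-sided 5% two-proportion test with 250 per arm would reject in about 9% of trials.
- m = 1% and 3%: 97.0% and 95.1%, rejecting in about 20%.

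The last two lines show only what unequal rates would do. The documents supply neither the rates nor that test.

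**The case against.** The strongest reply is that Section 7.3 is mainly a withdrawal rule. Its heading includes withdrawals, its sentence ends with the patient leaving follow-up, and the rest of the section concerns who stops attending and why. On that view 'endpoints' means end of participation, no implant is called failed, and an analyst can count revisions alone. Survivorship is also not among the objectives in Section 3. This reading is tenable and cannot be excluded. It does not settle the matter, because a revision-only count still lacks the later status of knees withdrawn on day 0 for an instrument fault. Section 7.3 itself goes on to ask for every effort to bring all patients back.

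Three stronger readings are tempting, and the documents do not support them:

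- **A reader might infer that survivorship will be derived from Section 7.3.** Section 9b does not cite that section, and Section 7.3 does not mention survivorship.
- **A reader might infer a bias against Group B.** The sensor stays in use there through rotation, release and rechecking of loads (Section 5 and Appendix II), against a blinded recording before closure in Group A, so more faults are plausible. But no malfunction rate or mode is given, faults at activation would not grow with time in the knee, and equal rates produce no difference. The rejection rates in Step 4 further need a between-arm survivorship test that Section 10 does not name.
- **A reader might infer that the words on implants reach other joints.** In a single-knee protocol they most naturally mean any component of the study prosthesis.

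**Conclusion.** The concern holds in a limited form. Section 7.3 gives a fault of a single-use trial insert the same status and the same consequence as implant removal or revision, survivorship is promised without a definition, and nothing in the text available to me separates the two events. On one reading a sound knee is counted as failed on day 0; on the other it drops out on day 0. Neither gives implant survival in all operated knees.

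The size is unknown. Under the assumed rates (2% revision, 0.5% to 2% malfunction) the failure reading understates survivorship by 0.5 to 2 percentage points. The end-of-participation reading loses 2.5 to 10 of 500 knees from follow-up, with little bias if those knees behave like the rest. No between-arm bias is established. This is a clarification worth making before the data are analysed. It does not show that the trial's main comparisons are wrong.

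**What to change.** In Section 7.3, separate the two events, and put the survivorship definition in Section 10:

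1. The survivorship event is removal or revision of a component of the study knee, timed from the date of surgery, which Section 9c already uses as day 0.
2. Intra-operative VERASENSE malfunction is a device-performance outcome, reported by arm as a count over the knees in which the sensor was used. It is neither a survivorship event nor a reason for censoring.
3. Malfunction does not trigger withdrawal. These patients stay in scheduled follow-up and in their allocated group. Without this sentence the first two changes cannot work, because the later revision status would not be collected.

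The cost is a few sentences. One malfunction item on the case report form may be needed: the safety form in Section 8 takes only adverse clinical events attributed to the procedure or the device, so a harmless fault might go unrecorded. The affected patients must be followed (2.5 to 10 in all under the assumptions above), and no combined failure count would be reported.
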